4.3 Subject Recruitment and Screening

Subjects who have been diagnosed with early AD or MCI, will be identified and informed about our study by our neurologist, [name], or any other trained neurologist. Neurologists will follow the guidelines suggested by the American Academy of Neurology, assessing for functional impairment and behavioral/neuropsychiatric symptoms to establish MCI or AD (Petersen *et al* 2018, McKhann *et al* 2011) according to the following inclusion criteria:

- Probable MCI or AD consistent with criteria outlined in (McKhann *et al* 2011, Petersen *et al* 2018).
- Modified Hachinski Ischemia Scale (MHIS) score of <= 4.
- Mini Mental State Exam (MMSE) scores of 12-26.
- Short form Geriatric Depression Scale (GDS) score of <= 6.
- PET scan confirming amyloid plaque load.

Should the patient agree to participate, a written permission will be asked to allow the treating physician to forward their name and contact information to the research investigators. The patients may also be given the contact information for the researchers, so that they may contact them if they are interested in participating. [name] or any other participating neurologist will document in the subject's medical record that permission has been obtained for the study team to contact the subject about enrollment in this study. [name] will enroll patients with moderate AD (MMSE scores: 12-18) who are not subject to higher risk of adverse effects due to mental impairment. PET scans are routinely conducted to confirm AD and are not expected to affect the safety of the FUS treatment.

Patients will be screened using the iNYP database on a password-protected computer with a secure ethernet connection. Discussion with subjects regarding research participation will take place in a private area (i.e., a patient exam room). All procedures related to the research study will also be carried out in a private room. The data acquired during research procedures will be anonymized and encrypted, and immediately removed from the ultrasound systems and transferred to the secure endpoint using an encrypted portable hard drive. After the transfer is complete, the imaging data will also be removed from the portable drive. Focus groups will not be used for this study. Subject privacy will be protected as described in attached HIPAA form.

4.4 Early Withdrawal of Subjects

4.4.1 When and How to Withdraw Subjects

Patients may withdraw at any time during the procedure by notifying the lead investigator and explaining the reason. Withdrawal at any time will result in partial withdrawal of the reimbursement/compensation, according to the compensation scheme per visit (see informed consent form).

4.4.2 Data Collection and Follow-up for Withdrawn Subjects

Data will be collected from the researchers involved in this protocol and stored in an encrypted computer. Follow-up for withdrawn subjects will be subjected to the time point they withdrew.

5 Study Device

5.1 Description

The system consists of two parts: (i) ultrasound unit for sonication and real-time passive acoustic monitoring (Sonic Concepts and Verasonics) and (ii) neuronavigator (Rogue Research) providing real-time

guidance. The guidance is achieved by registration of the physical space to the preloaded MRI that is displayed on the screen. The registration is achieved by the infrared camera reflecting the position of the subject tracker secured close to the brain. The transducer with a passive cavitation detector or an array transducer embedded is attached on the mechanical arm and the position varies depending on the brain structure to be sonicated. The transducer carries a tool tracker so its relative position to the brain can be seen on the screen. Once the transducer is locked at the position of interest the sonication begins. Real time monitoring of microbubble activity during sonication will be achieved via passive acoustic detection or passive acoustic mapping. B-mode ultrasound image will be acquired using the Vantage system for anatomical information and the mechanical index (MI) will be maintained below 0.1, well below the FDA limit of 1.9 MI. This investigative device will be operated in conjunction with microbubbles (Lantheus Definity) administered intravenously.

5.2 Treatment Regimen

The investigational device will be operated at acoustic parameters demonstrating safe and effective BBB opening in NHP followed by microbubble injection. The Definity microbubble dosage with an FDA guideline is 10 μ l/kg. The acoustic parameters for BBB opening are based on our NHP studies [17]-[21] and correspond to an I_{SPPA} of 2.81 W/cm², I_{SPTA} of 56.3 mW/cm² and a mechanical index (MI) of 0.4. These parameters produce safe and reproducible BBB opening in NHPs, as shown in our animal study report (appendix 6.1). These values are well below the limits set by the FDA for ultrasound imaging applications (I_{SPPA} < 190 W/cm², I_{SPTA} < 720 mW/cm² and MI < 1.9, respectively). To minimize the risk to subjects, we will use multiple simulation packages (e.g., kWave and SimSonic) in the treatment planning stage, in order to estimate the minimum attenuation coefficient through the subject's skull. We will use location-specific attenuation maps and perform a range of simulations (n = 10/package) to get a range of estimations. We will then choose the minimum attenuation estimation, which would lead to the minimum delivered dose possible.

5.3 Allocation to Treatment

This is a single arm, non-random trial.

5.4 Subject Compliance Monitoring

All the procedure will be performed in the hospital and patient compliance will be advised and monitored by researchers and/or healthcare providers.

5.5 Prior and Concomitant Therapy

Although BBB opening is reversible and transient, it may lead to unintended diffusion of pharmaceutical molecules into the brain parenchyma. To avoid such potential effects, non-critical medications will be withheld prior to treatment and until closure of the BBB is confirmed (at least 24 hours before and after the procedure). For critical medications, medication withholding will be judged based on the subject's diagnosis, condition, and medication type.

5.6 Packaging

The ultrasound transducer and the associated electrical components, i.e. function generator, power amplifier, and hydrophone, will be gathered in a mobile cart. The Vantage system with a linear array probe also will be in another mobile cart. All components will be connected prior to the patient's arrival and will be checked by two investigators to ensure smooth operation and safety.

The neuronavigation system along with the accompanying equipment, i.e. infrared camera, reflecting beads, holders etc., will be packed separately and gathered in a mobile cart. The parts will be assembled following the patient's arrival and the imaging beads will be attached to the patient's head and the transducer to allow for real-time neuronavigation.

New packages of Definity microbubbles will be shipped from Lantheus Medical Imaging Inc and will be used in conjunction with the ultrasound transducer to temporarily open the BBB. Definity microbubbles will be freshly activated before sonication and will be withdrawn using a 1-ml syringe to reach the clinical dose (10 μ l/kg) right before the IV injection.

New packages of Dotarem will be shipped from Guerbet LLC. Dotarem will be used as an MRI contrast agent to detect areas in which the BBB has opened. It will be administered according to manufacturer's guidelines at the recommended dose (0.2 ml/kg).

All study drugs will be provided free of charge to research participants.

5.7 Blinding of Study

There is no blinding, and the safety and the effectiveness will be compared with the contralateral treatment site of the patient.

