6.4 Visit 4/5

Follow-up visits will be required three weeks (± 1 week) and three months (± 2 weeks) after treatment to assess long-term safety, amyloid plaque load and cognitive function through behavioral tests. Two follow-up PET/CT scan using Amyvid (¹⁸F-Florbetapir) will be performed; one 3 weeks (± 1 week) post-FUS and one 3 months (± 2 weeks) post-FUS, to test for potential reduction in the amyloid plaque load. A blood sample will be also collected through an intravenous catheter or a finger prick, to test for long-term changes in blood chemistry and cell count. One follow-up visit following a single FUS treatment was deemed sufficient by the attending neurologist.

7 Statistical Plan

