7.1 Sample Size Determination

Successful methodology will be concluded if the BBB opening is safely opened in the PFC region in at least 75% of the cases as evidenced on MRI. The scan with the BBB opening will be compared to the scan before BBB opening for each patient. The data will be statistically analyzed with parametric paired Student's t-test. Power analysis shows that for a detectable difference of 200 mm³ (after BBB opening - before BBB opening) and a standard deviation of 50 mm³, at least 6 subjects are needed to report a result at the level of α =0.05 and Power=0.95.

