8.6.1 Data Monitoring Committee (if applicable)

The safety of the BBB opening using ultrasound and microbubbles has been confirmed by previous nonhuman primates studies, which revealed no adverse effects, permanent damage, or behavioral change following repeated treatments using low-intensity ultrasound and clinically-relevant microbubble doses. Ongoing clinical trials using this technique have not reported any acute adverse effect in either of the participants. However, long-term effects in the human brain have not been investigated to date.

To ensure the long-term safety in our study, the investigators will monitor and collect the data for processing and analysis while [name] will be present to assess the safety of the patient during FUS application. [name] will be present during the trial and will assess the subject's clinical status during therapy. In the case of an allergic or any other reaction to the therapy, the study will be immediately discontinued. Resuscitation equipment will be readily available in the study room, in case of a serious adverse event. Subjects will be monitored with follow-up MRI scans to confirm BBB opening and closing. BBB opening will be confirmed with an MRI scan immediately after the ultrasound treatment, while BBB closing will be confirmed three days later. Additional clinical evaluation will be performed by [name] or any other trained neurologist 3 months after the ultrasound treatment. Should the MRI brain scans of this study have incidental findings (e.g. brain tumor or potential structural abnormality) the subject will be immediately withdrawn from the study and directed for clinical care. Incidental findings will be communicated with both the subject and the subject's personal primary care physician.

Cognitive function will be assessed by [name] using appropriate tests before, during, and after the treatment.

9 Data Handling and Record Keeping

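### No masked MRI read is planned for the 75% (5 of 6) opening rule, which has no stated cut-off and which one changed call can reverse

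*Combined protocol and SAP*

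**What the plan says.** - **Blinding and comparator.** Section 5.7: "There is no blinding, and the safety and the effectiveness will be compared with the contralateral treatment site of the patient". Nothing limits this to subjects or operators, and no other section describes a masked, independent or second read of the images.
- **Design.** Section 5.3: "This is a single arm, non-random trial".
- **Success rule.** Section 7.1 calls the method successful if the barrier is "safely opened in the PFC region in at least 75% of the cases as evidenced on MRI". No volume or intensity that counts as opened is given.
- **A second comparator.** Section 7.1 also says "The scan with the BBB opening will be compared to the scan before BBB opening for each patient", and section 7.2 repeats a before/after comparison of gadolinium enhancement by paired t-test.
- **Scans.** The baseline MRI is without gadolinium (3.1, 6.1). The day-0 and day-3 MRIs are done with and without it (3.1, 6.2, 6.3). The target is the prefrontal cortex (PFC); the hemisphere is not stated (6.2).
- **Who looks at the images.** Section 8.6 has one neuroradiologist examine the MRI scans promptly, within two weeks at most, in a context of monitoring and incidental findings. The same section allows a radiologist at the treatment session. Section 8.6.1 says that "the investigators will monitor and collect the data for processing and analysis". No section says who makes the opening call.

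**The concern.** A single-arm sonication cannot be masked to the subject or the operator. The image read is a separate matter. Both hemispheres are on the same image, so a reader can mark enhancement on each side before being told which was treated. As written, section 5.7 gives this up without saying why.

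The read is open to expectation. Opening has no stated cut-off, and section 2.2 places the chosen setting near the opening threshold, so some calls may be equivocal. A reader who knows the planned focus could take a vessel or noise there for an opening, an error that favours the study's stated conclusion. With six patients a single such call can decide the result. The rule in section 8.5, under which failure to open in 3 subjects leads to a submission to the FDA, depends on the same call.

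**Working it through.** **1. The plan's own sample size, to see whether it is affected.** Inputs from section 7.1: "detectable difference of 200 mm³", SD 50 mm³, α 0.05, power 0.95, n = 6. The paired t-test power comes from the noncentral t distribution with n − 1 degrees of freedom and noncentrality d√n, two-sided.
- If 50 is the SD of the difference, d = 200/50 = 4. Power is 0.909 at n = 3 and 0.998 at n = 4.
- If 50 is the SD per scan with no correlation, the SD of the difference is 50√2 = 70.7 and d = 2.83. Power is 0.950 at n = 4 and 0.9996 at n = 6.

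Four would be enough on either reading, so six is conservative. Masking a read changes none of these inputs.

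**2. The 75% rule in whole patients.** 0.75 × 6 = 4.5, so at least 5 of 6 are needed. 4/6 = 66.7% fails and 5/6 = 83.3% passes. The exact 95% interval for 5/6 runs from 35.9% to 99.6%.

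**3. Is the side hidden from anyone?** Section 5.7 excludes blinding, and sections 7.1, 7.2, 8.6 and 8.6.1 provide no masking. The documents therefore do not keep the side from the reader. Equally, they do not say that the reader knows it.

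**4. What false calls could do.** Assume that every true opening is read correctly, that the safety part of the rule is met, and that each true failure is independently called open with probability q. The documents give no value of q; 0.1 to 0.3 is assumed.
- 4 true openings, 2 failures: at least 1 false call is needed, P = 1 − (1 − q)².
- 3 true openings, 3 failures: at least 2 false calls are needed, P = 3q²(1 − q) + q³.

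| q | 4 true openings | 3 true openings |
|---|---|---|
| 0 | 0 | 0 |
| 0.1 | 0.190 | 0.028 |
| 0.2 | 0.360 | 0.104 |
| 0.3 | 0.510 | 0.216 |

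Without fixing the number of true openings, let the true rate be p. The rate read as open is π = p + (1 − p)q, and P(at least 5 of 6) = 6π⁵(1 − π) + π⁶.

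| True rate p | q = 0 | q = 0.1 | q = 0.2 | q = 0.3 |
|---|---|---|---|---|
| 50% | 0.109 | 0.164 | 0.233 | 0.319 |
| 60% | 0.233 | 0.301 | 0.378 | 0.464 |
| 75% | 0.534 | 0.594 | 0.655 | 0.717 |

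**5. What the tables do not show.** The q = 0 entries assume no false calls at all, which a masked reader would not achieve. The gain from masking is the drop from one q to a smaller one. For example, with 4 true openings, a fall from 0.3 to 0.1 would lower false success by 51 − 19 = 32 points, and a fall from 0.2 to 0.1 by 36 − 19 = 17 points. Neither drop is known.

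**6. The rule in section 8.5.** With exactly 3 true failures, one false call leaves only 2 recorded, so the rule is not triggered: P = 1 − (1 − q)³ = 27%, 49% and 66% at q = 0.1, 0.2 and 0.3.

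**The case against.** The strongest case against the point is that this is an unblinded feasibility study in six patients, that section 5.7 is one sentence which does not describe the MRI read, and that masking may not work here.

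- **Who reads.** A reader might infer that the opening call is made knowing the side, by the investigators who ran the sonication. The documents do not support that. The person making the call is not named, and the sentence in 8.6.1 on processing data belongs to a paragraph on long-term safety. Because names are removed, it also cannot be told whether the MRI reader attends the session. What stands is that nothing prevents the reader from knowing.
- **Re-masking.** Coding files cannot re-mask an analyst who operated the device or a reader who has already done an unmasked read. This is correct. The masked marking has to come first, by someone who was not at the session.
- **Comparator.** The success rule sits beside a before/after comparison, not a contralateral one. With no gadolinium at baseline, that scan identifies itself and its place in the order cannot be hidden. This is also correct, and the two comparators must be reconciled.
- **Cut-off.** Masking without a definition of opened leaves an arbitrary call. Agreed; both are needed.
- **Faint openings.** The plan expects a difference of 200 mm³ with SD 50 mm³, so equivocal calls may be rare. That is possible, but it is a planning assumption that the study has yet to test.
- **PET.** Section 6.4 repeats the PET scans "to test for potential reduction in the amyloid plaque load", but amyloid load is not an endpoint in sections 3.2 to 3.4 and the 75% rule does not use it. PET masking is therefore optional.

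**Conclusion.** The point holds as a gap in the plan. No masked read is provided for the MRI call behind the 5-of-6 rule, the call has no stated cut-off, and one changed call from 4 to 5 reverses the conclusion. These statements rest on the documents alone.

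The size of any bias is unknown. The probabilities of 19%, 36% and 51% with 4 true openings, and 3%, 10% and 22% with 3, depend on assumed q, independent calls and a fixed number of true openings. Reading them as the effect of masking would be wrong, because a masked reader also makes false calls. It would also be too strong to say that masking removes the bias: the image itself may give clues, and section 7.2 still lets the method of analysis depend on the results. The sample size is unaffected. The improvement is cheap and worth making in a study whose main claim is a count out of six.

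**What to change.** Reword section 5.7 along these lines:

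> Subjects and operators are not blinded. The neuroradiologist who examines the study MRIs (section 8.6) does not attend the sonication. The day-0 contrast MRI is coded and, if the same hemisphere is always treated, randomly mirrored left to right. Before the side is revealed, this reader marks and measures enhancement in both PFCs against the cut-off stated in section 7.1. A case counts as opened only if the marked enhancement lies in the side and target later revealed. The side is then unlocked and the prompt safety review proceeds without delay.

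With it:
- State in section 7.1 the cut-off that defines opened, fixed before the first read. The 200 mm³ there is a planning difference and does not serve as one by default.
- Apply the same side-masked marking to the day-3 MRI where it does not delay the closure read, since section 5.5 ties the withholding of medication to confirmed closure. Masking is weaker there, because the reader has learned the side at day 0.
- Reconcile the contralateral comparator in 5.7 with the before/after comparator in 7.1 and 7.2, given a baseline MRI without gadolinium.
- Masking PET for date and side is optional.

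The cost is protocol wording, coding of one or two contrast MRIs per subject and a short marking step. No reader, scan, visit or patient is added, because section 8.6 already allows another radiologist to attend the session. The downside is the coding work and imperfect masking.

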5.8 Receiving, Storage, Dispensing and Return

5.8.1 Receipt of Study Device

The device will be delivered to the operating room from the storage room in the investigative site by the researchers prior to the procedure.

5.8.2 Storage

The ultrasound system including the focused transducer and the Vantage system will be stored in a room equipped with a locker and will be kept under in temperature till usage.

The neuronavigator system will be stored in the same locked room with the ultrasound system, and will also be kept in room temperature till usage.

Definity microbubble vials will be stored in a hospital grade fridge under 4 °C till usage. Microbubbles will be removed from fridge before the patient's arrival, to allow them acquire room temperature.

Dotarem contrast agents will be stored in a locked drawer in the MRI unit and will be kept in room temperature till usage.

5.8.3 Dispensing of Study Device

The physician performing the procedure will dispense the microbubbles and MRI/PET contrast agents to the patient, and the other researchers will deliver the ultrasound device from the storage room to the procedure room.

5.8.4 Return or Destruction of Study Device

The device should be returned to the following address if damaged: [name].

6 Study Procedures

After patient screening based on the selection criteria, the eligible patients will sign the consent form and fill the information form for the study, be scanned in the MRI for treatment planning, and then the sonication procedure. [name], MD at the Taub Institute of Alzheimer's Disease and Aging at Columbia, will be guiding this clinical application. The subjects will first be diagnosed and referred to the Presbyterian Hospital at Columbia University Medical Center. Six (6) patients will be asked to participate in this initial feasibility and safety study. The subjects will have to meet the following criteria: 1) 50 years old or older,

2) diagnosis of early AD or MCI at minimum (assessing criteria described in section 4.1), and 3) ability to provide informed consent. Approvals and consent forms approved by the Clinical Trials Office (CTO) and the Institutional Review Board (IRB) of Columbia University will be obtained through an IRB approved study.

6.1 Visit 1

All subjects agreeing to participate will undergo the following series of procedures in 4 or 5 visits. In the first visit, a high-resolution MRI scan (without gadolinium contrast agents) will be acquired prior to BBB opening on the 3T MRI for pre-treatment planning and screening purposes. Also, a blood draw and a PET/CT scan with Amyvid (¹⁸F-Florbetapir) will be performed to assess the baseline biomarkers and amyloid plaque load and before the treatment.

6.2 Visit 2

In the second visit, BBB opening will be attempted in a designated facility in the hospital using the described FUS system. First, a baseline cavitation signal will be obtained prior to microbubble injection. Then, an intravenous injection of Definity microbubbles under the FDA guidelines will be administered as a bolus or via a syringe pump and the cavitation signal will be monitored and recorded during sonication at acoustic parameters well below the FDA safety limit (MI = 0.4). In this EFS, we will target the prefrontal cortex (PFC). PFC has been shown to be affected by AD pathology, leading to deficits in attention, spatial memory and planned movements. Although we do not aim to treat AD in this EFS, PFC was selected as the targeted structure due to its relevance to this condition, its size and ease of targeting with our singleelement transducer. A follow-up MRI (with and without contrast) will be acquired the same day after BBB opening to ensure treatment safety and efficacy. Finally, two blood samples will be collected before and after treatment through an intravenous catheter or a finger prick. Blood analysis will be performed to test whether there are acute changes in the blood test results due to the FUS application. Based on our animal studies, there is an acute increase in reticulocytes, platelets and eosinophils after FUS treatment, possibly due to the BBB restoration process. Blood samples will be used to test whether these changes in blood chemistry occur also in humans. Blood samples will be stored and analyzed to detect potential changes in Alzheimer's Disease biomarkers and other compounds that may exit the brain parenchyma because of the blood-brain barrier opening (e.g. exosomes). All time points will be compared to baseline acquired during screening.

6.3 Visit 3

A follow-up MRI (with and without contrast) will be performed three days (± 1 day) after treatment to confirm BBB closure and to assess safety. A blood sample will be collected through an intravenous catheter or a finger prick, to test for short-term changes in blood chemistry and cell count.

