4.2 Exclusion Criteria

Exclusion criteria include surgeries and other pathologies not associated with AD, as outlined in the following list:

- Contraindication for MRI.
- Contra-indication history or hypersensitivity to MRI contrast agents (e.g., Dotarem) or microbubbles (e.g., Definity).
- Prior brain surgery, including deep brain stimulation.
- Metallic implants.
- Moderate or severe uncontrolled hypertension.
- Abnormal coagulation profile, e.g. hemophilia A or B.
- Coagulopathy or under anticoagulant therapy.
- History of stroke or cardiovascular disease.
- Active gingivitis, herpes simplex, hepatitis, tuberculosis, and minor skin or respiratory infections.
- History of seizure disorder.
- History of asthma or allergies to food or medication with significant symptoms in past 3 years.
- Severe brain atrophy.
- Inability to comply with the procedures of the protocol, including follow-up MRI scans.
- Pregnancy or lactation.
- Impaired renal function with estimated glomerular filtration rate (eGFR) <30 mL/min/1.73m² provided by a standard blood test 2-4 weeks prior to the ultrasound treatment.
- Active infection/inflammation.
- Acute or chronic hemorrhages, i.e. > 4 lobar microbleeds, and no siderosis or macrohemorrhages.
- Tumors or space occupying lesions.
- Meningeal enhancements.
- Intracranial hypotension.

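### The acute blood analysis at Visit 2 names the screening sample as its only reference and should name the same-day post-minus-pre difference

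*Combined protocol and SAP*

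**What the plan says.** Section 6.2 (Visit 2) states the purpose: "Blood analysis will be performed to test whether there are acute changes in the blood test results due to the FUS application". It gives an animal finding to look for in humans, that "there is an acute increase in reticulocytes, platelets and eosinophils after FUS treatment". For this, "two blood samples will be collected before and after treatment through an intravenous catheter or a finger prick". The section then ends its account of blood with the rule "All time points will be compared to baseline acquired during screening".

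The screening reference is the Visit 1 sample. Section 6.1 provides for "a blood draw and a PET/CT scan with Amyvid" to establish baseline values, at the visit whose MRI is "for pre-treatment planning and screening purposes". The time from Visit 1 to Visit 2 is not stated. The only timing given for any pre-treatment blood test is for kidney function in Section 4.2, "provided by a standard blood test 2-4 weeks prior to the ultrasound treatment", and nothing says that this is the same draw.

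Section 5.5 adds that "non-critical medications will be withheld prior to treatment", starting at least 24 hours before the procedure and lasting until closure of the barrier is confirmed. Critical medications are decided case by case.

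Section 5.3 describes a single-arm trial. Section 7 contains no analysis of blood measures.

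**The concern.** The question is about change caused by the procedure on the day, and the matching pair of samples is drawn. The one comparison rule in the text points to a different reference, taken at another visit and not required to be taken under withholding. Followed literally, it yields a change score that mixes any procedure effect with whatever happened between Visit 1 and the start of sonication.

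The design offers no other way to remove that part. There is no control group, and the contralateral comparison in Section 5.7 can serve imaging but not a systemic blood count. With six subjects, a shift before sonication could be read as confirming the animal finding, or could hide a real change.

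**Working it through.** **Decomposition.** For one subject let S be the screening value, A the Visit 2 value before treatment and B the Visit 2 value after treatment. Then

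B − S = (A − S) + (B − A).

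A − S is complete before sonication, so no part of it can be due to FUS. B − A is the acute change.

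**Withholding status at each draw (Sections 5.5 and 6.1 to 6.4).**

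| Sample | Non-critical medication |
|---|---|
| Visit 1 (S) | withholding not required |
| Visit 2 before and after (A, B) | withholding in force |
| Day 3 | withholding runs until closure is confirmed, which is the purpose of this visit's MRI; status at the draw is unclear |
| 3 weeks, 3 months | after the planned confirmation of closure |

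B and A match on medication; B and S need not. The 3-week and 3-month samples match S better than A.

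**Bias, illustration only.** The documents give no effect size, standard deviation (SD) or test for blood, so there is no figure of the plan's own to reproduce. The power statement in Section 7.1 concerns MRI opening volume. Assume n = 6, a paired t-test, two-sided alpha 0.05, and a mean shift A − S of d, in units of the SD of B − S. The rejection probability comes from the noncentral t distribution with 5 degrees of freedom and noncentrality d√6.

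With no true FUS effect:

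| Shift d | Probability of a false acute effect |
|---|---|
| 0 | 0.05 |
| 0.25 | 0.08 |
| 0.5 | 0.17 |
| 0.75 | 0.32 |
| 1.0 | 0.51 |

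With B − A the shift drops out and the rate returns to 0.05.

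Masking works the same way. A true change of 1.5 SD has power 0.83 with no shift, 0.51 with an opposing shift of 0.5 SD (net 1.0) and 0.17 with an opposing shift of 1.0 SD (net 0.5).

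**Precision, illustration only.** With equal variance σ² at each time and correlation ρ between two samples, the variance of their difference is 2σ²(1 − ρ). So

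SD ratio (screening to same-day) = √[(1 − ρ_screen) / (1 − ρ_same-day)],

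and its square is the ratio of subjects needed for equal precision.

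| ρ same-day | ρ screening | SD ratio | Subject ratio |
|---|---|---|---|
| 0.9 | 0.5 | √(0.5/0.1) = 2.24 | 5.0 |
| 0.9 | 0.7 | √(0.3/0.1) = 1.73 | 3.0 |
| 0.9 | 0.8 | √(0.2/0.1) = 1.41 | 2.0 |
| 0.8 | 0.7 | √(0.3/0.2) = 1.22 | 1.5 |
| equal | equal | 1.00 | 1.0 |

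Every correlation here is assumed. The gain depends on the same-day pair being more highly correlated than the screening pair. That is plausible, but the documents do not establish it.

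**The case against.** The strongest reply is that the plan already implies the right comparison. Drawing blood before and after treatment, followed at once by the aim of testing for acute change, suggests a before-after analysis. The screening rule comes later, directly after the sentence on stored samples and disease biomarkers, and does not say that it excludes other comparisons. The pre-treatment sample is itself one of the time points compared with screening, so drift and withholding would be visible and B − A follows by subtraction. This stands in part. A reader might infer that the plan rules out the same-day contrast, and the text does not support that. The defect is that the contrast is not named, which leaves the choice open after data from six subjects have been seen.

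A reader might also infer that every later sample should be referred to the Visit 2 pre-treatment value. That would be unsound at 3 weeks and 3 months. The Visit 2 sample falls within the withholding period and those samples follow its planned end, so the switch would put the medication difference into the long-term contrast.

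A third tempting reading is that the screening reference costs two to five times as many subjects. That holds only with the same-day correlation fixed at 0.9 and the screening correlation between 0.5 and 0.8. At 0.8 against 0.7 the factor is 1.5, and at equal correlations there is no cost.

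Two further limits stand. The same-day pair does not isolate FUS from the microbubble injection and saline flush. Nor does it exclude gadolinium if the second sample follows the MRI, because the draw times are not given. And although Sections 6.2 to 6.4 allow either a catheter or a finger prick, nothing says that a subject will switch between them; changing the baseline would not address that in any case.

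**Conclusion.** The point holds as a gap in the stated analysis; the sample collection is adequate. For the acute question, post minus screening contains a term that arises before sonication, and the single-arm design cannot separate it otherwise. The same-day difference removes that term with samples already planned.

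Neither the size nor the direction of the bias can be obtained from the documents. The false-positive figures (0.05 rising to 0.51 as the assumed shift goes from 0 to 1.0 SD) and the SD ratio (1.0 to about 2.2) show only what would follow from the stated assumptions.

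A reader might take this as a threat to the trial's main result. Sections 3.2 to 3.4 do not support that: blood measures are not among the listed endpoints, safety is assessed by MRI and neurocognitive tests, and Section 7.1 judges success on MRI. This is a worthwhile improvement to an exploratory analysis.

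**What to change.** In Section 6.2, with a matching line in Section 7.2:

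- State that the acute effect is assessed by the within-subject Visit 2 difference, post-treatment minus pre-treatment.
- Report post minus screening and pre minus screening as secondary. The latter shows directly how much moved before sonication.
- Keep screening as the reference for the 3-week and 3-month samples.
- Show the day-3 sample against both baselines.
- Record the time of each draw and the withholding status at that draw, so that the contrasts can be interpreted.

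The change of contrast costs a few sentences and no new samples or visits. As a minor separate suggestion, use the same collection route within a subject where possible. That would touch the wording of Sections 6.1 to 6.4 and is not needed for the main change.
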